8.4.12 Time to an intercurrent event in the Initial Treatment Period

See Section 3.9 for the definition of an intercurrent event.

Time to an intercurrent event (in days) during the Initial Treatment Period will be calculated as:

Min (Date of intercurrent event, Date of Week 16 visit) – Date of first dose of study medication + 1.

Participants who discontinue the study without experiencing an intercurrent event prior to Week 16 visit will be censored at the date of discontinuation. That includes participants who discontinue from the study for reasons other than Adverse Event and Lack of Efficacy.

Participants who reach the Week 16 Visit without experiencing an intercurrent event will be censored at the date of the Week 16 Visit. Participants will be censored at Baseline if there is no Post-Baseline visit.

Time to an intercurrent event will be estimated and presented using the Kaplan-Meier product-limit method for each treatment group.

Kaplan-Meier plots of time to initiation of systemic rescue therapy will be presented by treatment group. In these Kaplan-Meier plots, the line will start at 0 and will increase over time, representing time to intercurrent event.

The median time to an intercurrent event, including the 2-sided 95% confidence interval, will be calculated for each treatment. Comparisons of bimekizumab vs placebo will be analyzed using a log-rank test stratified by Hurley Stage at Baseline and Baseline antibiotic use.

8.4.13 Hidradenitis Suppurativa Symptom Daily Diary (HSSDD)

See Section 8.3.3 for details on HSSDD Baseline and weekly average definitions and derivations.

Percent change from Baseline in HSSDD responses for worst and average skin pain score is defined as

$$\text{Percent change from Baseline} = 100 \times \frac{\text{Post Baseline HSSDD score} - \text{Baseline HSSDD score}}{\text{Baseline HSSDD score}}$$

Change from Baseline in each HSSDD item (worst skin pain, average skin pain, smell or odor, itch at its worst, and amount of drainage or oozing) score will be summarized using descriptive statistics by treatment group and visit, based on weekly averages. The table will display descriptive statistics for the Baseline, followed by descriptive statistics for the change from Baseline for all visits. Percentage change will be summarized for the worst and average skin pain items.

Additionally, change from Baseline in each HSSDD item will be evaluated by treatment group at Week 16 via continuous empirical cumulative distribution function (eCDF) plots showing the absolute change from Baseline on the horizontal axis and the cumulative percent of participants experiencing that change on the vertical axis.

Change from Baseline in Worst Skin Pain score and Worst Itch score will additionally be summarized by visit and by analgesic and antihistamine use status (Section 6.4.2), respectively.

HSSDD response based on clinically meaningful change for the worst skin pain item is defined as at least a 3-point reduction from Baseline in HSSDD among study participants with a score of ≥ 3 at Baseline, based on weekly averages.

The number and percentage of responders based on clinically meaningful change for the worst skin pain item will be summarized by treatment group and visit.

The number and percentage of participants who were responders based on clinically meaningful change at any timepoint in the Initial Treatment Period will be summarized by treatment group for the worst skin pain item.

HSSDD response for the worst skin pain and average skin pain items is defined as at least a 30% reduction and at least a 1-point reduction from Baseline among study participants with a score of ≥ 3 at Baseline. The number and percentage of responders for each item will be summarized by treatment group and visit.

The number and percentage of participants who were responders (based on the 30% improvement and 1 point improvement definition) at any timepoint in the Initial Treatment Period will be summarized by treatment group for the worst skin pain and average skin pain items.

The number and percentage of participants that complete the HSSDD will be calculated for each visit by treatment group. A participant will be counted as completing the HSSDD at a visit if the minimum number of daily entries is present to calculate the weekly average (see Section 8.3.3). The percentage will be based on the number of participants in the RS. A participant will be considered a completer at a visit if the weekly average can be calculated for that visit.

8.4.14 Hidradenitis Suppurativa Symptom Questionnaire (HSSQ)

The 4 items on the HS Symptom Questionnaire (HSSQ) assesses participants' perception of the core symptoms of HS experienced in the past 7 days - skin pain, smell or odor, drainage or oozing from HS lesions, and itch on an 11-point NRS.

The change from Baseline score is derived as post Baseline score minus Baseline score. A negative change score indicates a reduction in the score/improvement for the participant.

Summary statistics of the actual values and change and percentage change from Baseline values will be used to summarize each HSSQ item for each visit by treatment group. The table will display descriptive statistics for the Baseline, followed by descriptive statistics for the change from Baseline for all visits.

Additionally, change from Baseline in each HSSQ item will be evaluated by treatment group at Week 16 and at Week 48 via continuous eCDF plots showing the absolute change from Baseline on the horizontal axis and the cumulative percent of participants experiencing that change on the vertical axis.

Missing data for the continuous change from Baseline will be handled by using MI via the MCMC and monotone regression method specified in Section 4.2.1.3.

HSSQ response for skin pain item is defined as at least a 30% reduction and at least a 1-point reduction from Baseline in HS Skin Pain score [11-point numeric rating scale]) among study participants with a score of ≥ 3 at Baseline.

The number and percentage of responders for skin pain item will be summarized by treatment group and visit based on the MS.

The number and percentage of participants who were responders at any timepoint in the Maintenance Treatment Period will be summarized by treatment group for the skin pain score based on the MS.

Change from Baseline in skin pain score and itch score will additionally be summarized by visit and by analgesic and antihistamine use status (Section 6.4.2), respectively.

The number and percentage of participants that complete the HSSQ will be calculated for each visit by treatment group. The percentage will be based on the number of participants in the MS. The summary will be repeated where the percentage is based on the subset of participants who complete each particular visit. A participant will be considered a completer at a visit if each of the items are completed at that visit.

8.4.15 DLQI

See Section 8.3.2 for the derivation of DLQI total score.

A DLQI total score of 0 or 1 indicates no impact of the skin disease on health-related quality of life and will be summarized.

A participant is considered to have achieved the minimally clinical important difference (MCID) if their individual improvement (ie, decrease) from Baseline in total score is ≥ 4 . A 4-point improvement in the DLQI total score (DLQI response) has been reported to be meaningful for the participant (within-participant MCID). The summary of MCID will be restricted to participants with a DLQI total score of at least 4 at Baseline to ensure that it is possible for the participant to achieve the MCID.

The DLQI related efficacy variables are defined as follows:

- Change from Baseline in DLQI total score is defined as Post-Baseline DLQI total score minus Baseline DLQI total score.
- Percent of study participants achieving a DLQI total score of 0 or 1 is defined as the number of study participants with DLQI total score of 0 or 1 divided by the number of study participants in RS.
- Percent of study participants achieving a MCID in DLQI total score is defined as the number of study participants with improvement from Baseline in total score of 4 or more divided by the number of study participants in RS that have a Baseline DLQI total score of at least 4.

Missing data for the DLQI total score will be handled by using MI via the MCMC and monotone regression method specified in Section 4.2.1.3.

Change from Baseline in DLQI total score will be summarized using descriptive statistics by treatment group and visit. The table will display descriptive statistics for the Baseline, followed by descriptive statistics for the change from Baseline for all visits.

Frequency tables will be produced to show the number and percentage of DLQI responders for MCID for each visit by treatment groups.

The number and percentage of participants achieving a DLQI total score of 0 or 1 at each visit will be summarized descriptively using counts and percentages by treatment group and visit.

The number and percentage of participants that complete the DLQI total score will be calculated for each visit by treatment group. The percentage will be based on the number of participants in the RS. The summary will be repeated where the percentage is based on the subset of participants who complete each particular visit. A participant will be considered a completer at a visit if the total score is calculated at that visit.

A by-participant listing of the DLQI questionnaire, DLQI total score, change from Baseline and DLQI response for MCID and 0 or 1 data will be provided by treatment group.

8.4.16 Hidradenitis Suppurativa Quality of Life (HiSQOL)

The HiSQOL includes 17 items assessed using a 7-day recall period, grouped in 3 subscales: symptoms, psychosocial, activities and adaptation.

The assessment of each item of the HiSQOL is as follows:

Table 8–5: Hidradenitis Suppurative Quality of Life

HiSQOL Scoring	
Response	Score
Unable to do, due to my HS	4
Extremely	4
Very Much	3
Moderately	2
Slightly	1
Not at all	0
I normally do not do this, HS did not influence	0
I am not sexually active	0
I do not work or study	0
Unanswered	0

The HiSQOL total score is calculated by adding the score of each question. The maximum score is 68, and the minimum score is 0.

Subscale scores will be summarized for each of the 3 subscales. The maximum scores for the subscales are 16 (symptoms), 20 (psychosocial), and 32 (activities and adaptations), and the minimum score is 0 for all subscales.

For all scores, the higher the score, the more quality of life is impaired.

Summary statistics of the actual values and change from Baseline values will be used to summarize HiSQOL domain and total scores for each visit by treatment group. The table will display descriptive statistics for the Baseline, followed by descriptive statistics for the change from Baseline for all visits.

Additionally, change from Baseline in each HiSQOL subscale will be evaluated by treatment group at Week 16 and at Week 48 via continuous eCDF plots showing the absolute change from Baseline on the horizontal axis and the cumulative percent of participants experiencing that change on the vertical axis.

Missing data for the continuous change from Baseline will be handled by using MI via the MCMC and monotone regression method specified in Section 4.2.1.3. The imputed HiSQOL total score will be derived based on the imputed subscales.

The number and percentage of participants that complete the HiSQOL will be calculated for each visit by treatment group. The percentage will be based on the number of participants in the RS (or MS, as appropriate). The summary will be repeated where the percentage is based on the subset of participants who complete each particular visit. A participant will be considered a completer at a visit if the total score is calculated at that visit.

A by-participant listing of the HiSQOL questionnaire, HiSQOL responses, domain and total scores and change from Baseline will be provided.

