3.3 Definition of Baseline values

Section 8.3.3 details the derivation of the Baseline value for the HSSDD assessment. For all other assessments, the below applies.

A Baseline value for a participant is defined as the latest non-missing measurement for that participant up to and including the day of administration of first study medication, unless otherwise stated. If a Baseline assessment is taken on the same day as first administration of study medication, it is eligible to be used as the Baseline value, even in the case that the time of the assessment is recorded as taking place after the time of first study medication administration. This is considered acceptable as this measurement is still the best representation of the Baseline value of the given assessment since it is highly unlikely that the study medication could have an impact on any measurement in such a short period of time. However, such cases should be rare as study center personnel are instructed to do all assessments at the Baseline visit prior to administering study medication. One exception to this rule is plasma concentration of bimekizumab. If Baseline plasma concentration is measured at a time after the first administration of study medication, then it will not be eligible to be considered as a Baseline plasma concentration. Such cases will be discussed with the quantitative clinical pharmacologist.

For randomized participants for whom no start date of treatment is available, the Baseline value will be considered as the last available value on or before the randomization date.

If a Baseline measurement is missing or not collected, and a Screening value is available, the Screening value will be utilized as Baseline instead.

Baseline values for component scores should be computed using components from the same visit where the relevant measurements were recorded prior to dosing. For example, if the Screening visit has all of the components, but the Baseline visit is missing 1 or more components, the Baseline value for the component score should be calculated using the Screening visit values.

When the time of first dose is derived, it will be based on the first injection of study treatment, regardless of whether or not it is an active treatment.

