- If Q7 is marked as "no" or "not relevant" and Q7a is missing, a score of 0 is given.
- If Q7 is missing and Q7a is missing, Q7 is considered unanswered (see below for details on how this impacts the DLQI total score).

If 1 question is left unanswered, this is scored 0 and the scores are summed and expressed as usual out of a maximum of 30. If 2 or more questions are left unanswered, the questionnaire is not scored.

Change from Baseline in DLQI total score is defined as Week 16 DLQI total score minus Baseline DLQI total score.

8.3.2.1 Primary analysis of change from Baseline in DLQI Total score at Week 16

Missing data imputation described in Section [4.2.1.2](#) will be applied.

Change from Baseline in DLQI total score will be presented by treatment group. The analysis model will be based on an ANCOVA with fixed effects of treatment, Hurley Stage at Baseline, Baseline antibiotic use and Baseline value as a covariate. The least square mean (LSM), standard error (SE), and 95% CI for the LSM will be presented by treatment group. For the comparison between placebo and bimekizumab: the difference between the LSM, the associated 97.5% CI for the contrasts, and the corresponding p-value will be presented. If one dose regimen is tested at the 0.05 significance level as determined in Section [4.5](#), then the confidence interval will be 95% instead of 97.5% for that dose with a corresponding $Z_{\alpha/2}$ of 1.96. Estimand and intercurrent event details are specified in [Table 8–2](#).

8.3.2.2 Sensitivity analysis of change from Baseline in DLQI Total score at Week 16

A sensitivity analysis using the same analysis model as in Section [8.3.2.1](#) will be used, based on observed data. Estimand and intercurrent event details are specified in [Table 8–2](#).

8.3.3 Change from Baseline in Skin Pain score at Week 16, as assessed by the “worst skin pain” item in the HSSDD

The items on the HSSDD assess patients' perception of the core symptoms of HS experienced in the past 24 hours: pain, smell or odor, drainage or oozing from HS lesions, and itch on an 11-point numeric rating scale (NRS). Two items assess skin pain: worst skin pain and average skin pain.

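### HiSQOL scores each unanswered item as 0 with no limit on blanks, so a partly answered form scores too low and still counts as completed

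*SAP*

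**What the plan says.** SAP Section 8.4.16 describes the instrument: "The HiSQOL includes 17 items assessed using a 7-day recall period, grouped in 3 subscales". Items score 0 to 4. Table 8-5 gives 0 to four kinds of answered response: 'Not at all', an activity the participant does not normally do, not being sexually active, and not working or studying. It also gives 0 to 'Unanswered'.

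The total is a plain sum: "The HiSQOL total score is calculated by adding the score of each question". Its range is stated as "The maximum score is 68, and the minimum score is 0", and the direction as "For all scores, the higher the score, the more quality of life is impaired".

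On completion, the section says "A participant will be considered a completer at a visit if the total score is calculated at that visit". Missing HiSQOL change data go to multiple imputation (MCMC/monotone regression, Section 4.2.1.3), with the imputed total built from the imputed subscales. The section gives no number of blanks above which a subscale or total is left uncalculated.

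For the DLQI, Table 8-3 also scores an unanswered question as 0, but Section 8.3.2 adds a limit: "If 2 or more questions are left unanswered, the questionnaire is not scored".

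**The concern.** Scoring a blank as 0 assigns it the best possible answer. That is harmless if the true answer would have been 0, and otherwise it understates impairment. With no cap, the understatement grows with each blank, and nothing in the scoring rule turns a poorly answered form into a missing one.

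Three things follow:

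- Change from Baseline is shifted. Post-Baseline blanks look like improvement; Baseline blanks lower the starting value and look like worsening.
- The imputation planned in the same section is bypassed for those blanks, because a number already exists.
- The completion table cannot show the problem, since a form with several blanks still has a total and is counted as complete.

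If blanks were more frequent in one arm, or at one visit, the descriptive comparison of arms or visits would carry that difference as if it were quality of life.

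**Working it through.** **Reproducing the stated scale.** Inputs are from Section 8.4.16: 17 items, item maximum 4, total maximum 68, and "The maximum scores for the subscales are 16 (symptoms), 20 (psychosocial), and 32 (activities and adaptations".

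- Items × maximum: 17 × 4 = 68, which matches.
- Sum of subscales: 16 + 20 + 32 = 68, which matches.
- Implied items per subscale: 16/4 = 4, 20/4 = 5, 32/4 = 8, together 17.

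The scoring rule is therefore read correctly.

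**Effect of blanks.** If the k skipped items would have been answered at level m, the recorded score is the true score minus k × m. For a participant who would answer every item at level m, the true total is 17 × m, and the shift as a share of that total is k/17 whatever m is.

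| Level throughout | True total | 2 blanks | 5 blanks | 8 blanks |
|---|---|---|---|---|
| Slightly (1) | 17 | 15 (−2) | 12 (−5) | 9 (−8) |
| Moderately (2) | 34 | 30 (−4) | 24 (−10) | 18 (−16) |
| Very much (3) | 51 | 45 (−6) | 36 (−15) | 27 (−24) |

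As a share of the true total: 2/17 = 11.8%, 5/17 = 29.4%, 8/17 = 47.1%. Subscales are more sensitive because they are shorter: one blank symptom item can remove up to 4 of 16 points.

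**Direction.** With true change zero at level 2, 5 post-Baseline blanks give 24 − 34 = −10 (apparent improvement). Five Baseline blanks give 34 − 24 = +10 (apparent worsening).

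**Effect on a group mean.** If a proportion p of an arm has k blanks at level m, the arm mean at that visit moves by −p × k × m. The difference between two arms moves by −(p₁ − p₀) × k × m, which is zero if blanks are equally common and alike in both. The SAP gives no value for p, k or m, so the table shows what the rule does to a form, not an expected bias.

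**How the SAP treats its other instruments.**

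| Instrument | Rule for blanks | Limit |
|---|---|---|
| DLQI (8.3.2) | One blank scored 0 | 2 or more: not scored |
| PHQ-9 (10.4.3.5) | None tolerated | Any blank: score missing |
| TSQM-9 (8.4.23) | Rescaled to the answered items | Formulas cover at most one missing item per domain |
| HiSQOL (8.4.16) | Every blank scored 0 | None stated |

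Under the DLQI rule, the most that blanks can hide is 3 of 30 points (10%). The same cap on HiSQOL would limit the loss to 4 of 68 (5.9%). The HiSQOL rule as written sets no such bound.

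**The case against.** The strongest reply is that little depends on it. HiSQOL is an 'other' efficacy endpoint (Section 2.2.1.3), outside the testing sequence in Section 4.5 and absent from the nominal p-value list in Section 8.5. The planned outputs are descriptive. The listing in Section 8.4.16 includes questionnaire responses, so blanks can be found there even though the completion table does not count them. The SAP sets scoring rules instrument by instrument, so a difference from the DLQI is not in itself an error, and the HiSQOL scoring guide is not available to check against. Nothing shows how often items are skipped, or whether data capture allows it. All of this stands and limits the weight of the point. It does not remove it: Table 8-5 provides for unanswered items, and the rule applied to them has no limit.

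Three stronger readings are tempting, and the document does not support them.

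- A reader might infer that a wholly empty form scores 0, shows maximal improvement and counts as completed. The section plans imputation and reports completion as a percentage, which presupposes that a total is sometimes absent. The natural reading is that a questionnaire not done is missing and goes to imputation.
- A reader might see an asymmetry with Section 3.3, which says "if the Screening visit has all of the components, but the Baseline visit is missing 1 or more components, the Baseline value" is calculated from Screening values. That needs a blank scored 0 to count as a missing component, and needs HiSQOL to be collected at Screening. The SAP establishes neither.
- A reader might conclude that blanks should be replaced by the mean of the answered items. The SAP gives no basis for that with this instrument. It could produce non-integer subscale scores where Table 4-2 allows only integers among imputed values, and would average in zeros that mean 'not applicable'.

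**Conclusion.** The point holds for partly answered forms. Followed literally, Section 8.4.16 scores them too low wherever a skipped item's true answer is above 0, counts them as completed, and keeps their blanks out of the planned imputation. The bias in change runs towards improvement for post-Baseline blanks and towards worsening for Baseline blanks.

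The size per form is k × m points: 10 of 68 for 5 blanks at 'Moderately'. The size in the trial cannot be stated, because the frequency and balance of blanks are not given; with few blanks it would be negligible. What is affected is the descriptive domain and total summaries, the Week 16 and Week 48 subscale eCDF plots, and the completion table. The primary and secondary analyses are untouched. A biased comparison between arms would further require blanks to differ between arms, for which the document offers no evidence.

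**What to change.** In Table 8-5, separate 'Unanswered' from the valid zero responses, which stay at 0. Add a cap to Section 8.4.16. One option in line with the SAP's DLQI rule is that at most 1 unanswered item is scored 0; with 2 or more, the affected subscale(s) and the total are not scored and go to the planned imputation, with the total rebuilt from the imputed subscales as the section already provides. If the instrument's scoring guide sets its own cap, use that and cite it. Define a completer as a participant whose form meets the cap.

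The cost is a few lines of SAP text and an edit to the scoring program. The downside is slightly more missing HiSQOL scores, which the planned imputation already handles.
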